Weekly visits should occur within the visit window (\pm 1 day). If an evaluation is missed, reschedule and perform it as close as possible to the original date. If rescheduling becomes, in the investigator's opinion, medically unnecessary because the evaluation would occur too close to the next scheduled evaluation, it may be omitted.

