3.2.2 Secondary Endpoints

- Proportion of subjects achieving an LVOT gradient response of post-exercise peak gradient < 30 mm Hg
- Change in dyspnea symptom score from baseline to Week 12
- Change in pVO₂ and VE/VCO₂ from baseline to Week 12
- Change from baseline in LVEF 2-dimensional (2D) and 3-dimensional (3D), global longitudinal strain, and left ventricular fractional shortening (LVFS) from baseline to Week 12
- Change from Week 12 to Week 16 in post-exercise peak LVOT gradient
- Plasma PK profile of MYK-461 treatment

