All analysis and summary tables will have the analysis population sample size (i.e., number of subjects) in the column heading. All listings will be sorted for presentation in order of study site, subject identification and date of procedure or event.

The day of the first dose of study drug will be defined as Day 1.

Baseline value will be defined as the last non-missing value in date/time before the first dose of study drug is administered.

Missing data handling will be described in Section 7, 8, 9 and 10.

All laboratory data will be reported using International System of Units (SI).

The planned analysis visit window for weekly visits will consider +/- 3 days of the scheduled visit date based on the date of first exposure to the study drug. For a missed visit, the evaluation will be rescheduled as close as possible to the original planned visit, thus analysis windows have been designed to be all-inclusive. If more than one result is available for a particular visit window and results are equidistant from the analysis target date, the later result will be selected to break the tie. The associated visit window with corresponding visit is tabulated below.

Visit	Scheduled Visit Day	Visit Window
Day 1	Day 1	[1, 4]
Week 1	Day 8	[5, 11]
Week 2	Day 15	[12, 18]
Week 3	Day 22	[19, 25]
Week 4	Day 29	[26, 32]
Week 5	Day 36	[33, 39]
Week 6	Day 43	[40, 46]
Week 7	Day 50	[47, 53]
Week 8	Day 57	[54, 64]
Week 10*	Day 71	[65, 78]
Week 12*	Day 85	[79, 99]
Week 16	Day 113	[100, 116]

*CPET may be conducted between study visits 10 and 12, therefore the planned analysis window ranges from Day 65 to Day 99 with Day 85 set to the scheduled visit day. Note: The window is adjusted for visit 12; visit 10 will not be presented.

For any subjects who discontinued treatment prior to Week 4 dose adjustment, the subjects will not be presented in the treatment columns (initial dose/adjusted dose), however will be presented in the total column in the table.

If the “seconds” portion of the date/time variable is missing or not collected, it will be imputed as “:00”, as needed.

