8.1. Primary Efficacy Endpoint

The primary efficacy endpoint is the change from baseline to Week 12 in post-exercise peak LVOT gradient. Baseline is defined as the last non-missing measurement of post-exercise LVOT gradient prior to the first dose. Post-exercise peak LVOT gradient will be analyzed using a mixed-effect model with repeated measures (MMRM). All data available from baseline (Screening) to Week 16 (EOS) will be included and missing data will be accounted for by the MMRM model. The model will include the fixed categorical effects of timepoint: baseline, Week 4, Week 12 (end of treatment), and Week 16 (EOS). An unstructured covariance structure will be assumed unless model diagnostics suggest otherwise.

This model will provide least-squares (LS) mean estimates with their corresponding standard errors at each time point. Comparison between baseline and Week 12 (end of treatment) will be based on the LS mean difference obtained from the MMRM, and will be presented with its associated two-sided 90% confidence interval. Statistical significance of the difference versus baseline will be evaluated at the two-sided 0.10 level. The primary efficacy endpoint will also be descriptively summarized by each timepoint.

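### The SAP calls its analysis windows all-inclusive, but the Week 16 window closes at Day 116, so an end-of-study visit on Day 117 or later maps to no analysis visit

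*SAP*

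**What the plan says.** SAP section 4 (General Statistical Considerations) sets the base rule: "The planned analysis visit window for weekly visits will consider +/- 3 days of the scheduled visit date", counted from first exposure. Missed visits are to be rescheduled near their planned date, and from this the SAP draws its conclusion: "thus analysis windows have been designed to be all-inclusive". In the table that follows, Week 12 (target Day 85) runs from Day 79 to Day 99 and Week 16 (target Day 113) from Day 100 to Day 116. There is no later row, and no rule for a record that falls outside every window.

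Protocol 9.6 says "Weekly visits should occur within the visit window", which it sets at plus or minus 1 day, and then: "If an evaluation is missed, reschedule and perform it as close as possible to the original date". It gives no latest date for a rescheduled visit.

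Week 16 carries a secondary endpoint of its own (SAP 3.2.2): "Change from Week 12 to Week 16 in post-exercise peak LVOT gradient". It is also one of the four timepoint categories in the primary MMRM, for which SAP 8.1 says "All data available from baseline (Screening) to Week 16 (EOS) will be included and missing data will be accounted for by the MMRM model". SAP 8.2 counts a missing gradient at a visit as no response.

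**The concern.** The stated purpose of the windows is that a rescheduled visit still finds a place. That purpose fails at one edge, the upper end of the last window, and that edge holds the end-of-study visit. No later visit competes for those days, so nothing is gained by closing the window there.

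The edge matters because Week 16 exists to measure reversibility after a 4-week washout, while the window counts days from first dose, not from last dose. A subject who runs late at Week 12 and then has the full washout can fall outside. At stake are the Week 12 to Week 16 change, the Week 16 estimates and the Week 16 by-visit safety summaries, in parts of about 10 subjects each.

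**Working it through.** **Inputs.** Targets and windows: SAP section 4 table. Washout of 4 weeks, i.e. 28 days: SAP 3.1. On-site dose at the Week 12 visit: Protocol 9.5.6. About 10 subjects per part: SAP 4.1.

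**Step 1: reproduce the table's bounds.**
- Weeks 1 to 7 are target ± 3. Week 1, for example: 8 − 3 = 5 and 8 + 3 = 11.
- Where visits are further apart, the upper bounds are midpoints between targets. Week 8: (57 + 71)/2 = 64. Week 10: (71 + 85)/2 = 78. Week 12: (85 + 113)/2 = 99.
- The Week 16 lower bound is the next day, 99 + 1 = 100.
- The Week 16 upper bound is 113 + 3 = 116. Here the table goes back to target + 3.

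**Step 2: coverage by day.** Each window starts the day after the previous one ends, so every day from 1 to 116 belongs to exactly one visit. From Day 117 on, no day belongs to any. A Week 16 visit within the protocol tolerance (Days 112 to 114) is covered. The first uncovered visit is 117 − 113 = 4 days late.

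**Step 3: a late Week 12 visit followed by a full washout.** Assume that the last dose is taken at the Week 12 visit and that the washout is 28 days.

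| Week 12 visit (all accepted as Week 12) | Plus 28 days | Inside the Week 16 window? |
|---|---|---|
| Day 85 | Day 113 | yes |
| Day 88 | Day 116 | yes |
| Day 89 | Day 117 | no |
| Day 99 | Day 127 | no |

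The latest Week 12 day that fits is 116 − 28 = 88. Conversely, a Day 100 visit after an on-time Week 12 visit has only 100 − 85 = 15 days of washout and is accepted as Week 16.

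**Step 4: what a record on Day 117 or later touches, if the table is applied literally.**
- The Week 12 to Week 16 gradient change: no Week 16 value for that subject.
- The MMRM: the Week 16 value is missing, but the subject's baseline, Week 4 and Week 12 values stay in.
- The Week 16 responder summary: scored as non-response. If the late gradient was in fact below 30 mm Hg, this overstates loss of effect after washout.
- By-visit laboratory, vital-sign and ECG tables (SAP 9.2, 9.3, 9.5): no Week 16 entry.
- Not touched: the Week 12 values used in the primary comparison, the listings, and adverse event tables, which SAP 9.1 defines by dates relative to dosing.

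**Step 5: size.** One record is 1/10 = 10% of a part's Week 16 data.

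**The case against.** **Nothing says that late data are excluded.** SAP 8.1 takes in all data through Week 16 and labels that timepoint as end of study, so a programmer could use the nominal visit. This stands, and it limits the point: loss is what the table implies, not what the SAP states. But section 4 assigns visits by study day, and where the SAP wants nominal time, as for PK summaries in section 10, it says so. Two programmers could reasonably produce different Week 16 results.

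**The late Week 12 case is built from a boundary.** Day 99 is a midpoint, not a sign that Week 12 visits are expected two weeks late, and rescheduling is tied to the original planned date. No text tells sites to move a completer's Week 16 visit because Week 12 was late. The nearest support is the end-of-treatment-plus-4-weeks description of the last PK sample in SAP section 10. This stands in part. The case is an example, and the gap does not depend on it: any end-of-study visit from Day 117 on is unassigned.

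**Few visits should be affected.** The protocol allows plus or minus 1 day, grants no waivers and expects up to 112 days of conduct after screening. This stands; the documents give no frequency of late visits.

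**An open-ended window mixes washout lengths.** True, but the present window already does so at its early edge. As an illustration, assume that the half-life of about 8 days (Protocol 1.2.1, single doses in healthy men) applies. The fraction of drug remaining is 2^(−15/8) = 0.27 after 15 days, 2^(−28/8) = 0.09 after 28 days and 2^(−42/8) = 0.03 for a visit 14 days late. The early visits already accepted differ more from the planned washout (0.27 − 0.09 = 0.18) than that late one would (0.09 − 0.03 = 0.06).

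**Conclusion.** The point holds as an internal contradiction. The windows are said to be all-inclusive, and they are not from Day 117 on. The effect is confined to Week 16: a named secondary endpoint, one MMRM category, one responder summary and the by-visit safety tables. Each affected visit is 10% of a 10-subject part. The conclusion assumes that the table is applied as written; the Days 89 to 99 case also assumes that dosing continues to a late Week 12 visit and that 28 days of washout follow.

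A reader might infer more than the documents support:
- **That the SAP discards these records.** It does not say so; it leaves them without an assignment.
- **That the primary result is weakened.** The Week 12 comparison keeps its own data.
- **That each lost record widens the standard error by about 5%.** The factor √(10/9) = 1.054 applies to a mean over complete pairs. The planned MMRM still uses the subject's other timepoints, so this is not its loss of precision.
- **That late visits are informative because illness or adverse events cause them.** Neither document says why visits would be late.

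It is worth correcting before database lock because the remedy is trivial and delivers what the SAP says it intends.

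**What to change.** In the SAP section 4 table, change the Week 16 row from Days 100 to 116 to Day 100 through the last study visit. Every day from Day 100 on is then covered and no windows overlap. Alternatively, keep the row and add a sentence assigning the end-of-study visit to Week 16 by nominal visit, whatever its study day. If excluding later visits is intended, say so and remove the all-inclusive statement.

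With either of the first two options, list the actual days since last dose beside each Week 16 value, for example in the stress echocardiography listing, so that washout length is visible.

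The cost is one table cell or one sentence, plus a listing column. The last-dose date is already used for exposure (SAP 7.2.1), so no new data are needed. The small downside is some variation in washout length among the Week 16 values, which the listing shows.

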4.1. Sample Size

Approximately 10 subjects will be dosed in Part A and in Part B. The sample size is based on practical considerations and is consistent with this type of study. Ten subjects per group receiving MYK-461 will provide 80% power to detect a 30 mm Hg within-group change from baseline in post-exercise peak LVOT gradient and a > 99% power to detect a 50 mm Hg change (Table 3). This assumes a 1-sided $\alpha = 0.05$ and a common standard deviation of 35 mm Hg. The common standard

deviation of 35 mm Hg is based on observed data in patients with HCM and provokable LVOT (Nistri et al., 2012).

Table 3 Power for Showing a Difference versus Baseline with 10 Subjects^a

Difference Versus Baseline In Peak LVOT Gradient (mm Hg)	Power (%)
50	> 99
40	95
30	80
20	50

^a Calculations were made using nQuery 7.0 Advisor software.

4.3. Analysis Set

4.3.1. All Enrolled

The All Enrolled Population includes every subject who signed informed consent. Subjects in the all enrolled population will be analyzed according to the planned dose combination.

4.3.2. Efficacy Analysis Population

The Efficacy Analysis Population is defined as all subjects who receive at least 1 dose of MYK-461 and have primary or secondary endpoint data, including a baseline value and at least one post baseline value. All efficacy analyses will be performed on the Efficacy Analysis Population. Subjects in the efficacy population will be analyzed according to the planned dose combination.

4.3.3. Safety Analysis Population

The Safety Analysis Population is defined as all subjects who receive at least 1 dose of MYK-461. Safety analyses will be performed on the Safety Analysis population. Subjects in the safety population will be analyzed according to the actual dose combination.

4.3.4. Pharmacokinetic (PK) Analysis Population

The PK Analysis Population is defined as all subjects who received at least 1 dose of MYK-461 and have at least one detectable PK concentration. PK analyses will be performed on the PK Analysis Population.

4.3.5. PK/ECG Analysis Population

The PK/ECG Analysis Population is defined as all subjects who received at least 1 dose of MYK-461 and have detectable PK concentration and ECG data pre-dose.

5. Subject Disposition

Subject disposition will be summarized for the all enrolled population. A disposition of subjects includes the number and percentage of subjects for the following categories: subjects who were enrolled, subjects who failed screening, subjects who completed the study, subjects who discontinued from the study, will be summarized. Besides, number of subjects in safety set,

efficacy set, PK set and in PK/ECG set will be summarized as well. All percentages will be based on the number of subjects enrolled.

The reasons for study discontinuation will also be summarized in this table. The reason for study discontinuation includes the following: adverse event, death, lost to follow-up, non-compliance with study procedures/restrictions, pregnancy, study terminated by sponsor, withdrawal by subject and other.

Subject disposition data will be presented in a listing.

All protocol deviations, extracted from the clinical trial management system, will be presented in a listing. Significant protocol deviations will be further subset in a separate listing.

6. Demographics and Baseline Characteristics

6.1. Demographics

A summary of demographics and baseline information will be presented. The demographic characteristics consist of age (years), sex, race, and ethnicity. The baseline characteristics consist of baseline height (cm), baseline weight (kg), and baseline body mass index (BMI) (kg/m^2). Age is calculated as (date of informed consent – date of birth)/365.25.

Age (years), baseline height (cm), baseline weight (kg), and baseline BMI (kg/m^2) will be summarized using descriptive statistics. The number and percentage of subjects by age category (≤ 65 , > 65), sex (Male, Female), BMI category (< 25.0 , $25.0-29.9$, ≥ 30.0 kg/m^2), race (White, Black or African American, Asian, American Indian or Alaska Native, Native Hawaiian or Other Pacific Islander, and Other) and ethnicity (Hispanic or Latino, Not Hispanic or Latino), will also be reported. Percentages will be based on the total number of subjects in the enrolled set. In addition, reproductive status and Pregnancy test will be also summarized.

Subject demographic and baseline characteristics will be presented in a listing.

6.2. Medical History

Medical History will be mapped to system organ classes (SOCs) and preferred terms (PTs) using the Medical Dictionary for Regulatory Activities (MedDRA Version 19 or higher). The number and percentage of subjects with any medical history will be summarized overall and by decreasing frequency of MedDRA SOC. Within each SOC, PT will be sorted by alphabetical order. Percentages will be calculated based on number of subjects in the safety population.

Subject medical history data including specific details will be presented in a listing.

6.3. Inclusion and Exclusion Criteria

Subjects who failed inclusion and exclusion criteria will be presented in a listing.

7. Treatments and Medications

7.1. Prior and Concomitant Medications

All medications used within 30 days prior to the date of informed consent through the end of study (EOS) will be collected on the case report form (CRF). All medications will be coded according to the World Health Organization drug dictionary (WHODRUG June 2016 or later).

A prior medication is defined as any medication that is taken within 30 days prior to the first dose of study drug. A concomitant medication is defined as any medication that has a stop date that is on or after the date of first dose of study drug.

For the purpose of inclusion in prior and/or concomitant medication tables, incomplete medication start and stop dates will be imputed as follows:

Missing start dates (where UK, UKN and UNKN indicate unknown or missing day, month and year respectively):

- UK-*MMM*-*YYYY*: If the month and year are different from the month and year of the first dose of study drug, assume 01-*MMM*-*YYYY*. If the month and year are the same as the first dose of study drug month and year and the end date (after any imputation) is on or after the first dose of study drug, then assume the date of the first dose of study drug. If the month and year are the same as the first dose of study drug month and year and the end date (after any imputation) is prior to the first dose of study drug, then assume the end date for the start date;
- DD-*UKN*-*YYYY*/*UK*-*UKN*-*YYYY*: If the year is different from the year of the first dose of study drug, assume 01-*JAN*-*YYYY* of the collected year. If the year is the same as the first dose of study drug year and the end date (after any imputation) is on or after the first dose of study drug, then assume the date of the first dose of study drug. If the year is the same as the first dose of study drug and the end date (after any imputation) is prior to the first dose of study drug, then assume the end date for the start date.

Missing stop dates (where UK, UKN and UNKN indicate unknown or missing day, month and year respectively):

- UK-*MMM*-*YYYY*: Assume the last day of the month;
- DD-*UKN*-*YYYY*/*UK*-*UKN*-*YYYY*: Assume 31-*DEC*-*YYYY*.

If start date is completely missing and end date is not prior to the first dose, then the medication will be classified as both prior and concomitant. If the start date is completely missing and the end date is prior to the first dose of study drug, then the medication will be classified as prior. If the end date is missing, then the medication will be classified as ongoing. Medications for which the start and end dates are missing will be classified as prior and concomitant.

7.1.1. Prior Medications

The total number of prior medications and the number and percentages of subjects with at least one prior medication will be summarized by preferred term and by alphabetical order. All summaries will be performed using the safety set.

7.1.2. Concomitant Medications and Procedures

The total number of concomitant medications and the number and percentages of subjects with at least one concomitant medication will be summarized and presented by preferred term and will be sorted in alphabetical order. All summaries will be performed using the safety set.

Concomitant procedures will be mapped to SOCs and PTs using the MedDRA Version 19 or later and will be presented in a listing.

7.2. Study Treatments

Study medication will consist of MYK-461 immediate-release oral tablets, 2mg, 5mg, 10mg, and 20mg. All subjects in Part A will be assigned to a starting dose of oral MYK-461 based on body weight for doses ≥ 10 mg. Subjects who weigh ≤ 60 kg will start at 10 mg and subjects who weigh > 60 kg will start at 15 mg. Subjects in Part B will be assigned a starting dose of 2 mg. Each subject will receive oral MYK-461 at their determined starting dose QD beginning on Day 1 and continuing through Week 4. At Week 4, an individual subject's daily dose may be adjusted based on predetermined criteria. The subject will subsequently receive that dose from Week 5 through Week 12.

7.2.1. Extent of Exposure

Duration of treatment (days) is defined as the total number of days a subject is exposed to any study drug and will be presented as the total number of days from the first dose date (Day 1) to the last dose date (date of last dose minus the date of first dose + 1) as recorded on the Study Completion/Termination page on the CRF. If the last dose date on the Study Completion/Termination page is missing, or if a subject is lost to follow-up, but the study drug exposure at investigation site form confirms that the subject has taken study drug at a visit, the latest date of the exposure at investigation site on the CRF will be used.

Because study drug reduction may occur during the study, the exposure to study drug will also be characterized by cumulative dose (mg), which is defined as the cumulative number of dose taken by subjects.

The duration of treatment to study drug will be summarized for all subjects in the Safety set and will be presented in a table by summary statistics. The duration of treatment will then be classified into the following categories: > 0 week, ≥ 2 weeks, ≥ 4 weeks, ≥ 6 weeks, ≥ 8 weeks, ≥ 10 weeks, and ≥ 12 weeks and will be presented as the number and percentage of subjects in each duration category. Percentages will be computed from the number of subjects in the Safety set.

The total cumulative dose (mg) will be defined as the sum of the actual dose taken across all study days. Average daily dose is cumulative dose divided by total days on study drug. The average daily dose and cumulative dose will be summarized by descriptive summary statistics.

A summary of each subject's exposure will be presented in a listing.

7.2.2. Treatment Compliance

Study drug compliance will be calculated for each subject by taking into account whether a subject takes all doses of study drug as instructed. The number of tablets taken will be calculated by subtracting the number of tablets returned from the number of tablets dispensed.

The overall study drug compliance (%) will be calculated by dividing the actual cumulative dose taken at all visits by the planned cumulative dose prescribed for all visits and then multiplying by 100. The overall study drug compliance will be summarized.

Summary statistics on percentage of treatment compliance as well as the number and percentage of subjects in each compliance category (<75%, 75-85%, and greater than 85% compliant) will be presented overall. Percentages will be calculated out of the number of subjects who were dosed in the Safety set. A subject is considered compliant if overall study drug compliance is greater than or equal to 80%.

8. Efficacy Analysis

All efficacy analyses will be performed on the Efficacy Analysis Population.

